#### **17.1.11.1 Immunogenicity analytical method**

An ELISA based method will be used for the detection of potential anti-canakinumab antibody formation. Method specifics will be listed in the central laboratory manual. The detailed method description to assess immunogenicity will be described in the bioanalytical raw data of the study and in the respective Bioanalytical Data Report (BDR).

Missing data will be labeled as such in the Bioanalytical Data Report.

### **17.1.12 Specific Safety Rules**

#### **17.1.12.1 Pregnancy and assessments of fertility**

All pre-menopausal women who are not surgically sterile will have pregnancy testing assessed at the time points per the Assessment Schedule ([Table 8-1](#)). Additional pregnancy testing might be performed if requested by local requirements.

Serum HCG should be performed at screening and EOC1 visits and urine HCG at all other visits. A positive or equivocal urine HCG should be confirmed by serum HCG.

### **Assessments of Fertility**

Medical documentation of oophorectomy, hysterectomy, or tubal ligation must be retained as source documents. Subsequent hormone level assessment to confirm the woman is not of child-bearing potential must also be available as source documentation in the following cases:

1. Surgical bilateral oophorectomy without a hysterectomy
2. Reported 12 months of natural (spontaneous) amenorrhea with an appropriate clinical profile.

In the absence of the above medical documentation, FSH testing is required of any female participant regardless of reported reproductive/menopausal status at screening/baseline.

#### **17.1.12.2 Pregnancy reporting**

Refer to [Section 10.1.4](#) for guidance and actions to take if a female trial participant becomes pregnant.

#### **17.1.13 Specific Study Design Considerations**

As this treatment does have an extended half-life, the EOC2 visit will serve as the end-of-study visit for participants randomized to this cohort.

The content of this SAP is based on the protocol version v04 dated 15-Sep-2022.

For each completed cohort, the data analysis will be performed upon final database lock for the cohort, and the results will be reported upon completion of each cohort in an end of cohort report. This analysis will include all available study data collected from the completed treatment arms within the cohort (and data from previous cohorts where available and appropriate). The purpose of this analysis is to formally assess safety and efficacy and to ensure data cleaning and reporting occurs on a periodic basis.

Commercially Confidential Information

This study will include an external Data Monitoring Committee (DMC). The DMC will function independently of site investigators participating in the study. The purpose of the DMC is to assess the progress of the EXPLAIN-AD treatment cohorts and the safety data.

Clinical Study Report (CSR). CCI DMC deliverables (tables, figures, listings - TFLs) and further programming specifications are described in separate documents.

1.1 Study design

This is a randomized, placebo-controlled, participant- and investigator-blinded platform study in participants with MCI due to AD or mild AD who have evidence of peripheral inflammation.

The EXPLAIN-AD study uses a platform type design to investigate "multiple targeted therapies in the context of a single disease in a perpetual manner". Each investigational agent or batch of agents and matching placebo entered into the trial at a given time will be considered a unique cohort. The decision to include future cohorts is not dependent on performance of prior agents or cohorts. Each time a new cohort is introduced, agent-specific information will be added to the protocol as a substantial amendment and submitted to Health Authorities and Ethical Committees, as required by local regulations.

Each cohort in the study will undergo the same study evaluations and assessments. Each cohort will include a screening period (Day -60 to Day -8), followed by a baseline period of 7 days (Day -7 to Day -1), a treatment period of 20 weeks (Day 1 to Day 141), and a study completion evaluation [End of Cohort (EOC1)] approximately 30 days after the last agent administration (Day 171). For agents with longer half-lives, such as monoclonal antibodies, the same study design will be followed; however, an additional post-treatment follow-up visit (EOC2) will occur on Day 281.

Participants who meet the eligibility criteria at screening will have baseline assessments performed. All baseline safety evaluation results must be available prior to randomization. All participants will undergo assessments of cognition, neuropsychiatric symptoms and function (activities of daily living) at various time points throughout the duration of the trial.

[figure not shown]
Moreover, all participants will undergo CSF sampling at screening and following completion of 12 weeks treatment. In addition, blood samples will be collected throughout the study.

In addition, a sub-set of these same participants (up to 22 per investigational agent/matching placebo) will undergo PET CCI imaging at baseline and following completion of the first 12 weeks treatment. Alterations in activated microglia and astrocytes due to therapeutic intervention will be measured using a PET CCI PET imaging in this subset of participants and analysis of CSF and/or serum samples in all participants will provide measures of both central and peripheral inflammation following treatment with an investigational agent/matching placebo. An interim analysis of the PET CCI and CSF soluble biomarker data may be conducted following completion of the first 12 weeks of treatment.

For each investigational agent, one or more interim analyses may be conducted, as appropriate, to support decision making concerning the sponsor's clinical development projects in general, or in case of any safety concerns. The results of these analyses will not have any impact on study conduct.

The study design is described in Figure 1-1.

Figure 1-1 Study design schematic

B = Baseline R = Randomization EOC = End of cohort

Randomization for any participant can occur after informed consent is obtained and eligibility is confirmed, ideally as close to Day 1 as possible. Participants will be randomized into any of the treatment arms open to enrolment for which the participant meets the eligibility criteria

Treatment arm(s) will be defined for each cohort.

EOC2 visit only required for an extended half-life. For all other treatments, EOC1 will serve as End of Cohort visit.

Approximately n=86 participants were planned to be randomized in a 1:1 ratio (active:placebo) using an IRT system. The study was prematurely terminated after 34 participants randomized due to sponsor's decision.

The primary endpoint is the change in NTB total z-score at week 24.

1.2 Study objectives, endpoints and estimands

Objective(s)	Endpoint(s)		
Primary objective(s)	Endpoint(s) for primary objective(s)		
 To compare the effects of each individua agent vs. placebo on cognition in early AD 	 The Neuropsychological Test Battery (NTB) score at 24 weeks 		
Secondary objective(s)	Endpoint(s) for secondary objective(s)		
To investigate the safety (AEs) and tolerability of each individual agent vs placebo	 ECG measurements and findings Adverse events and serious adverse events Laboratory measurements Vital signs Prospective suicidality assessment (ideation and behavior) from electronic Columbia Suicide Severity Rating Scale (eC-SSRS) 		
To investigate the effects of each individual agent vs placebo in lowering central inflammation	Reduction of microglial activation measured by Positron-Emission Tomography CCI 18 kDa (PET CCI) following the initial 12-weeks of treatment in a subset of participants		
To explore the effects of each individual agent vs placebo on neuropsychiatric symptoms	 The Neuropsychiatric Inventory (NPI-D) total score at 24 weeks eNeuropsychiatric At-Home Caregiver assessment score at 12 weeks 		
To compare the effects of each individual agent vs placebo on function (activities or daily living)	The Everyday Cognition (ECog) scale at 24		
To compare the effects of each individua agent vs placebo on memory and executive function	 The NTB memory and executive function composites at 24 weeks DSST at 24 weeks eCognitive at-home assessment at 12 weeks 		
To determine the pharmacokinetics of each individual agent	 Agent concentration in serum (for biotherapeutic agents) or plasma (for low molecular weight agents) and in cerebrospinal fluid (CSF) Ratio of agent concentration in CSF to that in serum (for biotherapeutic agents) or plasma (for low molecular weight agents) 		
To determine the total target and immunogenicity of each individual biotherapeutic agent	 Commercially Confidential Information Anti-agent antibodies in serum (when applicable) 		

Commercially Confidential Information

Commercially Confidential Information

1.2.1 Primary estimand(s)

The primary aim of the study is to demonstrate the effect on cognition of each anti-inflammatory agent vs. placebo, as measured by the NTB response after the 24 week treatment period.

The primary estimand is the change in NTB total z-score at weeks 24.

2 Statistical methods

2.1 Data analysis general information

Data will be analyzed by Novartis Biostatistics and Statistical Programming personnel according to the data analysis section 12 of the study protocol as detailed in this analysis plan.

SAS® version 9.4 (or later version if available at time of analysis) will be used for all analyses.

Data from all patients who signed informed consent will be used in the analysis; no center effect will be assessed as it is expected to have small sample size of enrollment at each individual centers.

General analysis conventions

Unless otherwise specified: categorical data will be presented as frequencies and percentages; continuous data will be presented as n, mean, standard deviation (SD), median, 25th and 75th percentiles, minimum, and maximum.

2.1.1 General definitions

Investigational treatment or **investigational drug** refers to the investigational agent tested within each cohort.

Study treatment or study drug refers to the investigational agent or matching placebo.

Treatment or treatment group

For presentation in the outputs, **treatment** refers to:

ACZ885 or Placebo in cohort 1

Date of first administration of study treatment

The date of first administration of study treatment is derived as the first date when a nonzero dose of study treatment was administered as per the Dosage Administration CRF. The date of first administration of study treatment will also be referred as *start of study treatment*.

Date of last administration of study treatment

The date of last administration of study treatment is derived as the last date when a nonzero dose of study treatment was administered as per the Dosage Administration CRF. The date of last administration of study treatment will also be referred as *end of study treatment*.

Study day

Study day 1 for all assessments is taken to be the start of study treatment.

The study day for all assessments will be calculated as follows:

- 1. If date of assessment occurred on or after the start of study treatment, then Study day = Date of assessment Start of study treatment + 1.
- 2. If date of assessment occurred before the start of study treatment, then Study day = Date of assessment Start of study treatment.

The study day will be displayed in the data listings. If an event starts before the reference start date, the study day displayed on the listing will be negative.

Baseline

For safety evaluations, the last available assessment on or before the date of start of study treatment is taken as baseline assessment. In case time of assessment and time of treatment start is captured, the last available assessment before the treatment start date/time is used for baseline.

For safety parameters (e.g. ECGs), where the study requires multiple replicates per time point, the average of these measurements will be calculated (if not already available in the database) to determine the baseline. The associated time will be the time of the last replicate.

In rare cases where multiple measurements meet the baseline definition, with no further flag or label that can identify the chronological order, then the following rule should be applied: If values are from central and local laboratories, the value from central assessment should be considered as baseline. If multiple values are from the same laboratory (local or central) or collected for ECGs or vital signs, then the median should be considered as baseline.

If participants have no value as defined above, the baseline result will be missing.

For safety parameters other than ECG, scheduled pre-dose collections as well as unscheduled collections on Day 1 for which no time is available will be considered as pre-dose.

For ECG, if dosing time on study Day 1 or ECG time for scheduled pre-dose ECGs is missing, the pre-dose ECG will be considered as baseline. If a scheduled pre-dose measurement actually occurred post-dose, then the corresponding measurement will be treated and analyzed similar to an unscheduled post-dose measurement.

Unscheduled Assessment:

In general, descriptive summary statistics will not include unscheduled/repeat assessment.

For all analyses regarding abnormal assessments or analyses based on worst post–baseline value (e.g. laboratory, ECGs, vital signs), all post-baseline values will be included (scheduled, unscheduled, repeat). All unscheduled and repeat measurements will be included in listings.

Analysis visit window:

No time-window will be applied in this study.

In summary by visit the scheduled EOC1 and EOC2 (if available) visit will be included.

On-treatment assessment/event

The overall observation period will be divided into 2 mutually exclusive segments:

- 1. *pre-treatment period*: from day of participant's informed consent to before date/time of first administration of study treatment
- 2. *on-treatment period*: from date/time of first administration of study treatment to the last visit date EOC1 (or EOC2 if applicable)

Note: If dates are incomplete in a way that clear assignment to pre-, on-, post-treatment period cannot be made, then the respective data will be assigned to the on-treatment period.

Safety summaries (tables, figures) include only data from the on-treatment period with the exception of baseline data which will also be summarized where appropriate (e.g. change from baseline summaries). In particular, summary tables for adverse events (AEs) will summarize only on-treatment events, with a start date during the on-treatment period (*treatment-emergent* AEs).

For all safety data listings (e.g. ECG, lab, vital signs, AEs), data collected during the post-treatment period will be flagged.

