## **10 Safety monitoring and reporting**

### **10.1 Definition of adverse events and reporting requirements**

#### **10.1.1 Adverse events**

An adverse event (AE) is any untoward medical occurrence (e.g., any unfavorable and unintended sign [including abnormal laboratory findings], symptom or disease) in a participant or clinical investigation participant after providing written informed consent for participation in the study. Therefore, an AE may or may not be temporally or causally associated with the use of a medicinal (investigational) product.

The investigator has the responsibility for managing the safety of individual participant and identifying adverse events.

Novartis qualified medical personnel will be readily available to advise on trial related medical questions or problems.

The occurrence of adverse events must be sought by non-directive questioning of the participant at each visit during the study. Adverse events also may be detected when they are volunteered by the participant during or between visits or through physical examination findings, laboratory test findings, or other assessments.

Adverse events must be recorded under the signs, symptoms, or diagnosis associated with them, accompanied by the following information (as far as possible) (if the event is serious refer to [Section 10.1.2](#)):

1. The severity grade will be used to characterize the severity of the Adverse Events based on the this general guideline:
  - mild: usually transient in nature and generally not interfering with normal activities
  - moderate: sufficiently discomforting to interfere with normal activities
  - severe: prevents normal activities
2. Its relationship to the study treatment and investigational PET CCI radioligand. If the event is due to lack of efficacy or progression of underlying illness (i.e. progression of the study indication) the assessment of causality will usually be 'Not suspected.' The rationale for this guidance is that the symptoms of a lack of efficacy or progression of underlying illness are not caused by the trial drug, they happen in spite of its administration and/or both lack of efficacy and progression of underlying disease can only be evaluated meaningfully by an analysis of cohorts, not on a single participant
3. Its duration (start and end dates or ongoing) and the outcome must be reported
4. Whether it constitutes a SAE (see [Section 10.1.2](#) for definition of SAE) and which seriousness criteria have been met

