**Adverse events**

All information obtained on adverse events will be displayed by treatment group and participant.

The number (and percentage) of participants with treatment emergent adverse events (events started after the first dose of study medication or events present prior to start of double-blind treatment but increased in severity based on preferred term) will be summarized in the following ways:

- by treatment, primary system organ class and preferred term.
- by treatment, primary system organ class, preferred term and maximum severity.

Separate summaries will be provided for study medication related adverse events, death, serious adverse events, other significant adverse events leading to discontinuation.

The number (and proportion) of participants with adverse events of interest will be summarized by treatment.

A participant with multiple adverse events within a primary system organ class is only counted once towards the total of the primary system organ class.

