2.3 Patient disposition, demographics and other baseline characteristics

2.3.1 Patient disposition

Participant disposition will be presented using the Safety set for all participants and by actual treatment received. The following summaries will be provided:

- Number (%) of participants who completed treatment and those who discontinued the study treatment phase along with the primary reason for study discontinuation
- At IA only: Number (%) of participants who are still on-treatment (based on the 'EOC1 (or EOC2 if applicable) disposition page not completed)

Participant disposition data will be listed.

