2.7.1 Adverse events (AEs)

All information obtained on adverse events will be displayed by treatment and participant.

The number (and percentage) of participants with treatment emergent adverse events (events started after the first dose of study medication or events present prior to start of study treatment but increased in severity based on preferred term) will be summarized in the following ways:

- by treatment, primary system organ class and preferred term.
- by treatment, primary system organ class, preferred term and maximum severity.

Separate summaries will be provided for study drug related adverse events, death, serious adverse events, other significant adverse events leading to discontinuation.

A participant with multiple adverse events within a primary system organ class is only counted once towards the total of the primary system organ class.

In AE summaries, the primary system organ class will be presented alphabetically and the preferred terms will be sorted within primary SOC in descending frequency. The sort order for the preferred term will be based on their frequency in all participants.

In addition, for EudraCT requirements a summary of (1) Serious AEs and deaths, with number of occurrences and (2) Non-serious AEs, with number of occurrences will be produced (an occurrence is defined as >1 day between start and prior end date of record of same preferred term).

2.7.2 **Deaths**

All deaths will be listed using Safety set and post treatment deaths will be flagged. A separate listing of deaths prior to starting treatment will be provided for all screened participants.

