3.2 Secondary endpoint(s)

For the secondary endpoint, PET $^{\text{CCI}}$, a comparison between an investigational agent and placebo will be based on data from approximately 10 participants per arm. Assuming inter-participant variability of 20%-25%, the power to detect statistically significant treatment difference (using 1-sided α =-0.05) is shown in Table 3-2 below. For the 25% true mean reduction in microglial activation due to an anti-inflammatory agent vs. placebo, there is at least 87% power (assuming coefficient of variation is 25% or less).

Table 3-2 Power for treatment comparison using log-transformed PET CCI at week 12

Coefficient of variation (CV)	True mean reduction (active vs. placebo)	α (1-sided)	Power
0.2	30%	5%	99%
0.2	25%	5%	93%
0.2	20%	5%	78%
0.25	30%	5%	93%
0.25	25%	5%	81%
0.25	20%	5%	62%

The assumed sample size is n=20 (10 per arm)

4

Change to protocol specified analyses

The study was CCI stopped. Therefore, the IA planned after 24 patients complete PET TPSO at 24 weeks will not be conducted.

5 Reference

ICH E9(R1) Harmonized Guideline: addendum on estimands and sensitivity analysis in clinical trials to the guideline on statistical principles for clinical trials. Final version on 20 November 2019.

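### SAP 2.1.1 admits adverse events to the summary tables by start date alone, while SAP 2.7.1 and Protocol 12.5.2 also count pre-dose events that worsen after first dose

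*SAP*

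**What the plan says.** SAP 2.1.1 divides follow-up into a pre-treatment period (consent to just before first dose) and an on-treatment period (first dose to EOC1, or EOC2 where it applies). It confines safety tables and figures to on-treatment data, with an exception for baseline values. It then says of adverse events in particular that "summary tables for adverse events (AEs) will summarize only on-treatment events, with a start date during the on-treatment period", and gives these the label treatment-emergent.

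SAP 2.7.1, the section on the AE tables themselves, defines treatment-emergent events in two parts. The first is events that start after the first dose. The second is "events present prior to start of study treatment but increased in severity based on preferred term". The adverse events text in Protocol 12.5.2 has the same two parts, the second being "events present prior to start of double-blind treatment but increased in severity based on preferred term".

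Two other passages bear on which text should prevail. SAP 2.1 says the data are analysed "according to the data analysis section 12 of the study protocol as detailed in this analysis plan". SAP section 4, which lists departures from the protocol's analyses, reports one: "Therefore, the IA planned after 24 patients complete PET TPSO at 24 weeks will not be conducted". It does not mention the AE definition.

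**The concern.** The same term is applied to the same tables with two different meanings. A programmer who sets the treatment-emergent flag from the general definitions would use the start date alone. One who works from 2.7.1 would also compare severity before and after first dose.

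Safety against placebo is a secondary objective, and the AE tables are its main summary. Pre-dose adverse events can exist in the database, because Protocol 10.1.1 counts any untoward occurrence "in a participant or clinical investigation participant after providing written informed consent for participation in the study", and screening can begin on Day -60. A case is easy to picture. Every participant has a lumbar puncture at screening, Protocol 4.9 names headache and local pain among its usual adverse events, and headache is also among the events reported with canakinumab (Protocol 17.1.2.2.2). A screening headache that worsens on treatment could be counted under one rule and left out under the other.

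**Working it through.** There is no stated figure to reproduce. The check compares the two rules and then works out what one affected participant would do to a table.

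**Step 1. The rules side by side**

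| Event | SAP 2.1.1 | SAP 2.7.1 and Protocol 12.5.2 |
|---|---|---|
| Starts after first dose | counted | counted |
| Starts before first dose, does not worsen | not counted | not counted |
| Starts before first dose, worsens after it | not counted on its pre-dose start date | counted |

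Only the third row differs.

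**Step 2. Which text is out of line**

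SAP 2.7.1 and the protocol agree with each other. SAP 2.1 says the analysis follows protocol section 12, and SAP section 4 declares no narrowing of the AE definition. That leaves 2.1.1 as the outlier.

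**Step 3. When the counts would differ**

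Take one participant with an event that is mild before first dose and moderate after it. The result depends on how the event is held in the database:

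| Recording convention | Count under 2.1.1 | Count under 2.7.1 |
|---|---|---|
| One record, pre-dose start date kept, severity change captured | 0 | 1 |
| New record with a post-dose start date when severity rises | 1 | 1 |
| One record, one start date, one severity grade only | 0 | 0 (the rise cannot be seen) |

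The counts part only under the first convention. Neither document says which one is used.

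**Step 4. Size of the shift**

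Inputs: 34 participants randomised, planned ratio 1:1 (SAP 1.1). Arm sizes are not given, so an even split is assumed: 34/2 = 17 per arm. Shift in a term's incidence in one arm per affected participant = 1/n.

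- n = 17: 1/17 = 0.0588, or 5.9 percentage points
- n = 15 (assumed): 1/15 = 0.0667, or 6.7 points
- n = 19 (assumed): 1/19 = 0.0526, or 5.3 points
- no affected participant: 0

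The denominator in these tables is the safety set, meaning participants who received study drug, so it may be somewhat smaller than the number randomised.

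**The case against.** The strongest reply is that the two rules may give the same answer in practice. For the EudraCT summary, SAP 2.7.1 treats successive records of one preferred term as separate occurrences only when more than a day separates them. Such a rule is useful if a continuing episode can be split into back-to-back records, and a change in severity is a natural place to split. Judging the increase by preferred term also suggests comparing records across first dose. On that reading the worsened record starts on treatment and 2.1.1 already captures it. This is a fair hint but not proof. Protocol 10.1.1 has an event followed to resolution with its severity reassessed at each visit, which fits one continuing record at least as well. The recording details are left to the Site Operations Manual.

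A second reply is that the section specific to the AE tables should govern. But the sentence in 2.1.1 is itself specific to those tables and uses the word only, and the SAP text gives no rule of precedence.

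A third is that the exposed window is narrow. Conditions present at consent go to medical history, so only events that start between consent and first dose and then worsen are at issue. That stands.

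So do the limits on any loss. SAP 2.7.1 keeps every event in view at participant level: "All information obtained on adverse events will be displayed by treatment and participant". A worsening that ended treatment would still show in the disposition table of SAP 2.3.1, which covers those who "discontinued the study treatment phase along with the primary reason for study discontinuation". Worsening that makes an event serious can qualify as an SAE in its own right under Protocol 10.1.2. What could be missed is therefore mainly non-serious worsening, in the tables by preferred term and by maximum severity.

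**Conclusion.** The conflict in the text is real, and it lies in the current SAP. SAP 2.1.1 states a narrower rule than SAP 2.7.1 and the protocol, with no declared reason. Confidence is high on that and only on that.

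No effect on the counts has been shown. An effect needs an event that starts between consent and first dose, worsens afterwards, keeps its pre-dose start date, and has the severity change captured. The number of such participants is unknown and may be zero. Each would move one term in one arm by about 5.9 points if the arms hold 17 each. The tables are descriptive and the efficacy analysis is not involved, so this is a minor point.

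A reader might infer three stronger things that the documents do not support:

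- That the SAP declares no change from the protocol at all. It declares one, the cancelled interim analysis. What it does not declare is a change to the AE definition.
- That the sponsor chose to narrow the definition. SAP 2.7.1 repeats the protocol's rule, which points to a drafting slip in 2.1.1.
- That the AE tables will understate harm. This would require the recording convention and the data, and neither is in the documents.

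**What to change.** Change two adjoining sentences in SAP 2.1.1.

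1. Replace the whole AE sentence with: *AE summary tables will present treatment-emergent AEs as defined in Section 2.7.1, that is, AEs that start after first dose and AEs present before first dose that increase in severity after it.*
2. In the sentence before it, which confines safety summaries to on-treatment data apart from baseline values, add a second exception: *and AEs with pre-dose onset that increase in severity after first dose.*

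Replacing only the start-date clause would not be enough. The restriction to on-treatment events in the same sentence, and to on-treatment data in the sentence before, could still be read as shutting out an event with pre-dose onset.

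The cost is a short text edit. It needs no new data, no new analysis and no protocol amendment, because the protocol and SAP 2.7.1 already state the rule.
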